The study treatment doses administered at Visits 2 and 3 are considered as the “repletion phase” and any subsequent administrations (if ID persists) will be considered as the “maintenance phase”. The first dose of study treatment will be administered for all randomised subjects at Visit 2 while the subject is still hospitalised for the Index hospitalisation. It is recommended that the first dose of study treatment is administered on the same day as randomisation. To accommodate local hospital practice, the first dose of study treatment may be administered either on the same day or the day before the planned discharge day. Note that a planned overnight stay following study treatment administration does NOT fulfil the criteria of a serious adverse event (SAE) unless there is a medical reason for doing this. The subsequent administrations of study treatment will be done as part of the outpatient clinic visits at Week 6 (Visit 3), and at Weeks 12 (Visit 4) and 24 (Visit 5). Dosing at Week 6 (Visit 3) will be based on the iron need upon screening Hb and weight values to replete iron as described in Table 1 and only be done in subjects for whom Hb at Week 6 (Visit 3) ≤15 g/dL. Maintenance dosing at Weeks 12 (Visit 4) and 24 (Visit 5) is only for subjects in whom ID persists and for whom Hb ≥8 g/dL* and ≤15 g/dL at those visits. ID is defined as serum ferritin <100 ng/mL, or 100 ng/mL ≤ serum ferritin ≤299 ng/mL if transferrin saturation (TSAT) <20%. The serum pregnancy test must also be negative for the respective visit for females of childbearing potential. Subjects will be requested to return to the outpatient clinic for the administration of study treatment maximally 7 days after the date when the blood sample was drawn.

Study treatment will be prepared by an unblinded study personnel using black syringes and once prepared, study treatment should be administered immediately thereafter using a curtain (or similar) to maintain subject blinding. Each subject should be observed for adverse effects for at least 30 minutes following each injection of study treatment. The unblinded study personnel may be involved in performing screening activities. Following randomisation the unblinded study personnel will not be operationally involved in the study for the subject concerned other than the preparation and administration of study treatment and assessment and interpretation of post-randomisation laboratory test results.

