6. RANDOMISATION, BLINDING AND UNBLINDING PROCEDURES

6.1 Randomisation

All subjects enrolled must be identifiable throughout the study. The Investigator will maintain a list of subject numbers and subject names to enable records to be found at a later date.

Numbered study treatment packs will contain either FCM solution or placebo (i.e., normal saline) according to a computer generated randomisation plan.

Each eligible subject will be randomised to either FCM or placebo using a validated centralised procedure (IWRS) that automates the random assignment of treatment groups to randomisation numbers. Subject randomisation (1:1) will be determined by a minimisation algorithm including a random variable and accounting for the following stratification factors: sex, age (<70 years/≥70 years), HF aetiology (ischemic/non-ischemic), HF duration (newly diagnosed at Index hospitalisation/known documented HF prior to Index hospitalisation), country and centre. The system will allocate study treatment pack number(s) which should be used for the subject concerned. Details on how to randomise a subject will be found in the respective user manual.

The randomisation plan will be kept strictly confidential, accessible only to authorised persons, until the time of unblinding. If a subject discontinues from the study, neither the subject identification number nor the allocated study treatment pack numbers will be reused, and the subject will not be allowed to be re-randomised in the study.

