6.2 Blinding

This is a double-blind trial with randomisation concealment and neither the Investigator, the subject nor Sponsor (or representative) will be aware of the administered study treatment to each subject. The Vifor Pharma Safety Department will have access to the randomisation codes as will investigational sites should the need to unblind a subject arise.

As the FCM and placebo solutions differ in appearance and the study treatment boxes will not be blinded, unblinded study personnel not involved in any study assessments (other than assessment and interpretation of post-randomisation laboratory test results) will be responsible for handling the study treatment boxes, and preparing and administering the study treatment injections in black syringes and using a curtain (or similar) to maintain subject blinding. Unblinded personnel will make sure the subject is not able to observe the preparation of study treatment injections.

Post-baseline iron values should be seen only by the unblinded study physician, who will then be responsible for evaluating the parameters. This physician must review the parameters to confirm the subject well-being and follow guidance per Section [10.2.6](#).

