7.2.2 Dosing and Administration Guidelines

The dose of study treatment to be administered will be determined using the subject's body weight and Hb values based on a repletion and maintenance dosing scheme. Subjects will be administered study treatment as an undiluted bolus IV injection - a 10-mL vial of FCM contains 500 mg iron. The individual dose requirements (in mL) per visit are detailed in [Table 1](#). The doses of study treatment administered at Visits 2 and 3 are considered the repletion phase and any subsequent administrations (if ID persists) will be considered the maintenance phase. All administrations, including duration of injection, will be documented in the site source data and in the eCRF. Each administration of study treatment will be documented in the treatment accountability log kept by the unblinded person on site.

The IV bolus injection will be done using a black syringe. A curtain (or similar) will be used in addition to ensure that blinding of the subject is maintained. Injections will have a volume of 20 mL (1,000 mg iron or normal saline) or 10 mL (500 mg iron or normal saline) depending on the subject's Hb value and body weight.

In case a site has local regulations that prevent the use of a black syringe then the investigational site needs to provide an alternative acceptable procedure that will maintain the blind, whilst satisfying their local procedures. This alternative procedure must receive approval by the Sponsor on a site-by-site basis.

The following describes the procedure for the preparation and administration of study treatment.

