7.5.3 Accountability

The unblinded study personnel at each site is responsible for study treatment supplies. The study personnel will ensure that adequate records of the receipt, preparation, administration and return of the study treatment are kept and that the study treatment is used only for subjects enrolled in the study. All data regarding the study treatment (including kit and batch numbers) must be recorded in the eCRF and on any other relevant forms provided.

Each study site will maintain a treatment inventory/dispensing record for all treatments dispensed and returned. At the end of the study, 1 copy of the treatment inventory/dispensing record should be sent to the Sponsor for the central study file. The original will be kept in the site files.

After completion of the study, or if it is prematurely terminated, all unused materials will be returned to the Sponsor. The decision to destroy study treatment at site must be made by the Sponsor. If the study treatment is destroyed at site, the Investigator will forward the certificate of destruction to the Sponsor.

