12.7 Efficacy Evaluations

12.7.1 Primary

The primary outcome is the composite of recurrent HF hospitalisations and CV death up to 52 weeks after randomisation.

The HF hospitalisation and CV death rates per 100 patient-years of follow-up as adjudicated by the CEC, will be calculated by dividing the total number of HF hospitalisations, and CV deaths by the total follow-up duration of all subjects in each group. The rate ratio (95% CI and p-value) for this analysis will be analysed using a negative binomial model. Compared to the Poisson distribution, the negative binomial

distribution allows for different individual tendencies (frailties) with respect to their risks of repeat hospitalisations [41].

The negative binomial model will be adjusted for the following baseline covariates: sex, age, HF aetiology (ischemic/non-ischemic), HF duration (newly diagnosed at Index hospitalisation/known documented HF prior to Index hospitalisation) and country. A sensitivity analyses will be performed using an unadjusted model.

The primary outcome analysis will be performed on the FAS will use the CEC adjudicated events. A sensitivity analysis will be performed on the PP population set.

Descriptive statistics will provide, per treatment group, the total number of events and the number (%) of subjects with at least one event.

A graphical representation of the estimated cumulative hazard rate will also be provided.

As the analysis of HF hospitalisations could be confounded by the competing risk of death, a confirmatory analysis will be performed on the FAS population set using the joint frailty model in order to analyse repeat hospitalisation rate whilst accounting for their associated mortality rate [42].

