2.2. Randomisation Methodology

This is a double-blind trial with randomisation concealment, and neither the Investigator, the subject, nor the Sponsor (or representative) will be aware of the study drug allocated to each subject. The FCM and placebo solutions differ in appearance. Hence, unblinded study personnel not otherwise involved in any study assessments (efficacy or safety) will be responsible for preparing and administering the study drug injections. At the site level, study drug will be prepared by the unblinded team and assessments during follow-up will be done by the blinded team only. The Vifor Pharma Safety Department will have access to the randomisation codes, as will Investigational sites should the need to unblind a subject arise.

Each eligible subject will be randomised to either FCM or placebo using a validated centralised procedure [Interactive Web Response System (IWRS)] that automates the random assignment of treatment groups to randomisation numbers. Subject randomisation (1:1) will be determined by a minimisation algorithm including a random variable and accounting for the following stratification factors: sex, age (<70 years/≥70 years), HF aetiology (ischaemic/non-ischaemic/unknown), HF duration (newly diagnosed at Index hospitalisation/known documented HF prior to Index hospitalisation), country, and centre. The system will allocate study drug pack number(s) which should be used for the subject concerned. Details on how to randomise a subject will be found in the respective user manual.

A total of 1,100 subjects (550 per treatment group) will be randomised into the study.

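### Unblinded site staff may screen later candidates while minimisation balances on centre, which leaves a modest and cheaply closed gap in allocation concealment.

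*Protocol*

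**What the plan says.** **Who may screen.** The treatment section of the protocol synopsis says "The unblinded study personnel may be involved in performing screening activities". The next sentence sets the limit: "Following randomisation the unblinded study personnel will not be operationally involved in the study for the subject concerned", apart from preparing and giving treatment and reading post-randomisation laboratory results. The limit starts at randomisation and attaches to one subject at a time. It does not reach the next candidate.

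**What these staff know.** Protocol 6.2 explains why an unblinded team is needed: "As the FCM and placebo solutions differ in appearance and the study treatment boxes will not be blinded". Section 7.2.2 adds that "Each administration of study treatment will be documented in the treatment accountability log kept by the unblinded person on site", and section 7.5.3 that "The unblinded study personnel at each site is responsible for study treatment supplies".

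**How subjects are allocated.** Protocol 6.1: "Subject randomisation (1:1) will be determined by a minimisation algorithm including a random variable and accounting for the following stratification factors". The factors are sex, age group, HF aetiology, HF duration, country and centre. Neither document gives the probability attached to the random element or the factor weights.

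**What pulls the other way.** SAP 2.2 describes "unblinded study personnel not otherwise involved in any study assessments (efficacy or safety) will be responsible for preparing and administering the study drug injections" and reserves follow-up assessments for the blinded team. Protocol 6.2 likewise keeps unblinded staff out of study assessments other than post-randomisation laboratory review. Neither passage withdraws the synopsis permission to screen.

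**The concern.** A central web system conceals the upcoming assignment, but it cannot stop inference from past assignments when the algorithm corrects imbalance within centre. A person who knows that one arm is behind at the site has some information about the next allocation. If that person also helps decide which patients are put forward, and when, sicker or less sick patients can drift towards one arm.

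At stake is the comparability of the arms for the primary rate ratio. The primary model adjusts for sex, age, aetiology, "HF duration (newly diagnosed at Index hospitalisation/known documented HF prior to Index hospitalisation) and country". It includes no direct measure of severity such as natriuretic peptide, ejection fraction or NYHA class, so it would not remove selection on severity.

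**Working it through.** **1. The plan's own figure.** The documents give no figure for predictability. Their sample size supplies the standard error used in step 4. Inputs (Protocol 12.2 and synopsis): placebo rate 0.7 per year, rate ratio 0.75, dispersion 1, mean follow-up 11 months, 80% power, two-sided alpha 0.05. With the Zhu-Lakkis formula and the null variance taken at the reference rate:

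- V0 = (12/11)(2/0.7) + 2 = 5.117
- V1 = (12/11)(1/0.7 + 1/0.525) + 2 = 5.636
- n per group = (1.960√5.117 + 0.842√5.636)² / (ln 0.75)² = 499.8, i.e. 500
- 1,000/(1 − 0.09) = 1,099, i.e. 1,100

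The stated size is reproduced.

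**2. Predictability: set-up.** Minimisation (Pocock-Simon) was simulated on the six stated factors with 1,100 subjects at 100 sites (Protocol 5.1, about 11 per site) and 15 countries (SAP Table 4), 60 runs per setting. The guess uses only the site's own history: name the arm with fewer subjects there, and score ties as one half. Assumed, because the documents are silent: the probability of assigning the imbalance-reducing arm, the factor weights, the factor prevalences and the spread of site sizes.

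**3. Predictability: results with equal weights.**

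| Assignment probability | Correct, all enrolments | Correct when the site is unbalanced |
|---|---|---|
| 0.6 | 52.7% | 53.6% |
| 0.7 | 55.2% | 57.1% |
| 0.8 | 57.8% | 61.1% |
| 0.9 | 60.3% | 65.1% |
| 1.0 | 62.3% | 68.9% |

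The site is unbalanced for about 65-76% of enrolments. With purely random assignment (probability 0.5) the guess is right 50.2% of the time. A separate simulation with equal and with skewed site sizes gave 55-63% for probabilities 0.7-1.0, and 51-52% when centre was left out of the factors. If centre carried three times the weight of the others, the all-enrolment figure would be 55.6-71.7%.

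**4. Effect on the primary test.** Let g be the hit rate, d the proportional shift in event rate between patients steered to each guessed arm and the average, and f the share of enrolments steered. With no drug effect:

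RR = [1 − f(2g − 1)d] / [1 + f(2g − 1)d]

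The null standard error of log RR is √(5.117/500) = 0.101. Type I error is the probability that a normal variable with mean |ln RR|/0.101 falls outside ±1.960.

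| Share steered | g = 0.58, d = 0.10 | g = 0.60, d = 0.20 |
|---|---|---|
| 100% | 0.984/1.016 = 0.969; 6.2% | 0.960/1.040 = 0.923; 12.4% |
| 25% | 0.996/1.004 = 0.992; 5.1% | 0.990/1.010 = 0.980; 5.4% |
| 10% | 0.9984/1.0016 = 0.997; 5.0% | 0.996/1.004 = 0.992; 5.1% |

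Each cell gives the null rate ratio, then the two-sided type I error. The hit rates of 58% and 60% correspond to assignment probabilities of about 0.8 and 0.9.

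**The case against.** **The unblinded screener does not hold the decisions.** The Investigator obtains consent and reviews eligibility (Protocol 9.2.1.1), makes the final check before randomisation (9.2.3.9), judges exclusion criterion 26 and chooses when screening starts (Table 2, note 1). Section 6.2 says the Investigator does not know the treatment. This largely stands. An unblinded Investigator is named in 7.6.1, 9.2.3.11 and 9.2.3.13, but for post-randomisation laboratory review and dosing. What remains is indirect influence over whom to approach, bring forward or defer, and a final eligibility check cannot see patients who were never put forward.

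**Deferral has little reach.** Randomisation must happen during the index stay. Waiting changes the site-based guess only if another subject is randomised at that site meanwhile, which will be uncommon at about 11 subjects per site. This stands for deferral, but not for the choice of whom to approach.

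**A site blinding plan exists.** SAP Appendix I (PDSPR14) makes departure from it a major deviation. Its content is not in these documents, so whether it restricts screening is unknown, and the listed statistical consequence of a breach is none.

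**Selection would be visible.** A reader might infer that nothing planned could reveal steering. That goes too far. SAP 4.5.2 tabulates natriuretic peptides, ejection fraction, NYHA class, earlier AHF hospitalisation and creatinine by arm, and the subgroup models in 4.6.3 add such variables one at a time. These might show an imbalance, but none is designed to detect or remove selection.

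**Centre should not be a factor at all.** A reader might also infer this from its absence in the primary model. Balancing on centre and modelling country is a legitimate trade-off with so few subjects per centre, and the documents give no reason to reverse it.

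**Conclusion.** The gap is real and modest. The text lets people with a site's allocation history help screen later candidates, and balancing on centre makes the next arm about 53-62% predictable to them, given equal factor weights and an assignment probability of 0.6-1.0. Heavier weighting of centre would raise this; a larger random element would lower it. The documents do not say that one person handles every allocation at a site, but the log and supply duties put that information with the unblinded role.

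A reader might conclude that concealment has failed or that the trial runs at a 6-12% type I error. The documents do not support either. They show an opportunity and no sign that it was used, and the 6-12% range requires every enrolment at every site to be steered. With 10-25% steered, the error stays at about 5.0-5.4%. The case for acting rests on the very low cost of closing the gap, not on a large expected bias.

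**What to change.** Replace the synopsis sentence with: *Once the first subject has been randomised at a site, unblinded study personnel must not take part in pre-screening, screening, consent or eligibility decisions for any subject; these are done by the blinded team.* Align Protocol 6.2 and SAP 2.2 with it. Keep centre in the minimisation.

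The cost is less flexibility in who screens. The present permission is optional, SAP 2.2 already provides for a blinded team at site level, and neither the sample size nor any analysis changes.

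The wording helps only subjects not yet enrolled. The SAP accompanies protocol version 3.1 of 01 Apr 2020, and the COVID-19 provision covers only Visit 6, which suggests, without stating it, that enrolment had closed. In that case the sponsor can check delegation records for unblinded staff who screened after their site's first randomisation, and report the assignment probability and factor weights with the results.

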16.3 Study Termination92
17. POLICY FOR PUBLICATION AND PRESENTATION OF DATA94
18. REFERENCES.....95

LIST OF TABLES

	Page
Table 1	Study Treatment Dosing Regimen.....7
Table 2	Schedule of Events.....16
Table 3	New York Heart Association Classification61

LIST OF FIGURES

	Page
Figure 1 Flow Chart	15

LIST OF APPENDICES

	Page
Appendix 1 Serious Adverse Event Form (Sample).....	99
Appendix 2 Report on Exposure to Medicines During Pregnancy (Sample).....	105
Appendix 3 Guidelines for Administering Informed Consent	107

LIST OF ABBREVIATIONS

AHF	Acute heart failure
ADR	Adverse drug reaction
AE	Adverse event
ARNI	Angiotensin receptor neprilysin inhibitor
BNP	Brain natriuretic peptide
CHF	Chronic heart failure
CI	Confidence interval
CEC	Clinical Endpoint Committee
CRO	Contract Research Organisation
CV	Cardiovascular
DMC	Data Monitoring Committee
DSMB	Data and Safety Monitoring Board
EC	Ethics Committee
ECG	Electrocardiogram
eCRF	Electronic case report form
EQ-5D	European quality of life – 5 dimensions
ES	Spain
FAS	Full analysis set
FCM	Ferric carboxymaltose
GCP	Good Clinical Practice
GMP	Good Manufacturing Practice
Hb	Haemoglobin
HF	Heart failure
HRQoL	Health-related quality of life
ICF	Informed consent form
ICH	International Council for Harmonisation
ID	Iron deficiency
IEC	Independent Ethics Committee
IRB	Institutional Review Board
IV	Intravenous

IWRS	Interactive web-based randomisation system
KCCQ	Kansas City Cardiomyopathy Questionnaire
LVEF	Left ventricular ejection fraction
MedDRA	Medical Dictionary for Regulatory Activities
NL	The Netherlands
NT-proBNP	N-terminal-pro-brain natriuretic peptide
NYHA	New York Heart Association
OR	Odds ratio
PP	Per-protocol set
PT	Preferred term
QoL	Quality of life
RCT	Randomised controlled trial
RSI	Reference Safety Information
SAE	Serious adverse event
SAP	Statistical Analysis Plan
SC	Steering Committee
SG	Singapore
SOC	System organ class
TSAT	Transferrin saturation
UK	United Kingdom
VAS	Visual analogue scale
WMA	World Medical Association
w/v	Weight per volume

1. INTRODUCTION AND BACKGROUND

Two major clinical trials (FAIR-HF and CONFIRM-HF) have demonstrated that the treatment with intravenous (IV) ferric carboxymaltose (FCM) improves functional capacity, exercise tolerance, symptoms and quality of life (QoL) in stable iron deficient subjects with heart failure (HF) [1,2]. Additionally, in the secondary analysis of the CONFIRM-HF trial, the treatment with IV FCM was associated with a significant 60% reduction of the risk of hospitalisations for worsening HF during the 12 month follow-up. Moreover, the recent meta-analysis of 5 trials with IV iron therapy in patients with stable HF (including 509 subjects receiving IV iron therapy in comparison with 342 subjects receiving placebo) has shown that IV iron therapy can reduce the risk of the combined endpoint of all-cause death or/and cardiovascular (CV) hospitalisation (odds ratio (OR) 0.44, 95% confidence interval (CI) 0.30-0.64, $P < 0.0001$), and the combined endpoint of CV death or hospitalisation for worsening HF (OR 0.39, 95% CI 0.24-0.63, $P=0.0001$) [3].

Acute heart failure (AHF) constitutes a clinically and economically challenging problem. The prognosis of these patients remains poor, and so far, major clinical trials have failed to improve outcomes in these patients. The current treatment of AHF remained virtually unchanged in recent decades. Iron deficiency (ID) is frequent among patients with HF and predicts poor outcome [4]. Although, there are premises that correction of ID in AHF patients could improve clinical outcomes, it has not been investigated to date.

We aim to investigate the effect of IV FCM, relative to placebo on recurrent HF hospitalisations and CV death up to 52 weeks after randomisation in iron deficient subjects hospitalised for AHF.

